5.3 Study Duration: 1 month

- The duration anticipated to complete all study procedures, including any long-term follow-up, and data analysis: 12 months

5.4 Use of radiation: N/A

5.5 Use of Center for Magnetic Resonance Research: N/A

## 6.0 Data and Specimen Banking

6.1 Storage and Access: The primary data collected and stored a password protected UMN PCs as outlined later. In addition the data file will be encrypted and password protected. All computer equipment is in a locked office of the PI at the UMN. Data exported for analysis will only be shared as a de-identified file. The primary identifying data file will be deleted after publication.

6.2 Data:

baseline clinical patient characteristics e.g. age, gender, medications.

- 6.3 Release/Sharing: No directly identifying PHI will be released outside the University of Minnesota.

## **7.0 Sharing of Results with Participants**

- 7.1 Patient will be informed of their personal results: benefit – no benefit.  
If requested by the participant the treating provider will be contacted to discuss the potential benefits of a cilostazol prescription.
- 7.2 Sharing of genetic testing: N/A

## **8.0 Study Population**

Patients with HFpEF are typically >55y/o with an equal gender distribution

### **Inclusion Criteria:**

>18 yrs

LVEF  $\geq$  50% (on last assessment, <2 years)

Diagnosis of HFpEF **or** Shortness of breath **and** NYHA Class  $\geq$  2 **and** one of the following:

1. pulmonary edema on chest imaging **or** documented on exam **or** on loop diuretics
2. NTproBNP >400 ng/ml in the last 24 months
3. HFpEF >50% hospitalization in the last 3 years
4. Qualitative echo: > mild diastolic dysfunction on echo report **and** > mild left ventricular hypertrophy **and** left atrial dilation or quantitative echo: left ventricular hypertrophy [men  $\geq$ 115 g/m^2, women  $\geq$ 95 g/m^2 or relative wall thickness >0.42 or any LV wall thickness >1.2cm **and** has LA dilation (>28ml/m^2)

### **Exclusion Criteria:**

<18yo

resting heart rate >100/min (assessed by pulse or ECG recorded in EPIC)

patients with LVEF <50% and advanced end-stage heart failure (NYHA 3 and 4)

symptomatic COPD on home O2

uncontrolled severe HTN as defined by BP >160/100 mmHg on two checks  $\geq$ 15 minutes apart

patients with life expectancy <6 months

end-stage liver cirrhosis

more than moderate valve disease

infiltrative myocardial disease (e.g. amyloidosis) or constrictive pericarditis or myocarditis

patients unable to participate in follow up

patients without baseline LVEF data > 2 years

pregnant patients or patients without reliable contraceptive agent (intra-uterine device, birth control implant, compliance with contraception injections or contraception pills) for the duration of study participation)

left ventricular outflow tract obstruction

MEDICAL PROTOCOL (HRP-590)

PROTOCOL TITLE: **Cilostazol for HFpEF**

VERSION DATE: 05.16.2020

bleeding dyscrasias, blood dyscrasias

Patients that take: ketoconazole, itraconazole, fluconazole, miconazole, fluvoxamine, fluoxetine, nefazodone, sertraline, erythromycin, clarithromycin or azithromycin

**Screening:**

Individuals will be screened or assessed for eligibility during a hospital admission at the UMN Medical Center or in the UMP cardiology outpatient clinics.

**9.0** Vulnerable Populations

*9.1* Vulnerable Populations:

Population / Group	Identify whether any of the following populations will be targeted, included (not necessarily targeted) or excluded from participation in the study.
Children	Excluded from Participation
Pregnant women/fetuses/neonates	Excluded from Participation
Prisoners	Excluded from Participation
Adults lacking capacity to consent and/or adults with diminished capacity to consent, including, but not limited to, those with acute medical conditions, psychiatric disorders, neurologic disorders, developmental disorders, and behavioral disorders	Excluded from Participation
Non-English speakers	Excluded from Participation
Those unable to read (illiterate)	Included/Allowed to Participate
Employees of the researcher	Excluded from Participation

Students of the researcher	Excluded from Participation
Undervalued or disenfranchised social group	Included/Allowed to Participate
Active members of the military (service members), DoD personnel (including civilian employees)	Included/Allowed to Participate
Individual or group that is approached for participation in research during a stressful situation such as emergency room setting, childbirth (labor), etc.	Excluded from Participation
Individual or group that is disadvantaged in the distribution of social goods and services such as income, housing, or healthcare.	Included/Allowed to Participate
Individual or group with a serious health condition for which there are no satisfactory standard treatments.	Included/Allowed to Participate
Individual or group with a fear of negative consequences for not participating in the research (e.g. institutionalization, deportation, disclosure of stigmatizing behavior).	Excluded from Participation
Any other circumstance/dynamic that could increase vulnerability to coercion or exploitation that might influence consent to research or decision to continue in research.	Excluded from Participation

9.2 Additional Safeguards:

Individuals who are ethnic minorities would not be excluded from this study if they were so inclined to participate. Subjects would be taken through the consent process as per usual if subject is an ethnic minority who is English speaking.

Individuals who are illiterate, would go through the consent as per usual; a witness would sign the consent form, documenting the consent process.

Undervalued or disenfranchised social group (transgender, LGBTQIA+ etc, person of color, etc.) would not be targeted but could be incidentally included if they met criteria and wanted to participate.

Individual or group that is disadvantaged in the distribution of social goods and services such as income, housing, or healthcare are not targeted but could be included. No compensation is provided for participating in this study; thus, subjects from these groups would not feel coerced to participate in order to obtain monetary compensation.

A subject might incidentally be a person with a military background, active or inactive duty. We do not see them in a setting where rank could operate to coerce them into participating.

Risks are minimized through compliance with the study protocol, adherence to the guidelines for selection of subjects, close monitoring of the subject status during the study and follow-up procedures. The sponsor provides training for research staff on this study protocol. This training, extensive knowledge of the protocol along with investigator and research staff experience aid in minimizing risks to subjects.

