### *2.2 Preliminary Data:*

Cilostazol is approved for the use in peripheral artery disease and has been used in patients with diastolic dysfunction-induced atrial fibrillation and HFpEF. This results in a symptomatic relief and significant reductions in the heart failure blood marker BNP (7,8). In our own clinical experience, cilostazol reduces HFpEF symptoms and lowers NTproBNP by about 25% to suggest a clinical benefit that is in line with the cilostazol-induced changes in BNP in patients with atrial fibrillation (7,8). No adverse effects were noted in our own HFpEF patients that chronically take cilostazol.

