## 4.0 Study Intervention(s)

### 4.1 Description:

We propose a n-of-1 study design using the standard dose cilostazol formulation of 100mg twice a day approved in peripheral vascular disease. The patients will be blinded and serve as their own controls with two crossovers (cilostazol – placebo – cilostazol - placebo). This exploratory study is neither designed nor powered to seek a change in

[figure not shown]

the drug approval and thereby does not require an FDA investigational new drug (IND) application (see section 4.1). The study aims to minimize in-person visits during the ongoing COVID-19 pandemic.

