**Detail the FDA exemption:**

After reviewing the information contained in your submission, we have concluded that your study, "Cilostazol for HFpEF," meets all of the requirements for exemption from the investigational new drug (IND) regulations and, therefore, an IND is not required to conduct your investigation.

The IND regulations [21 CFR 312.2(b)] state that the clinical investigation of a drug product, including a biological product, that is lawfully marketed in the United States, is exempt from the requirements for an IND if all of the following apply:

- (1) The investigation is not intended to be reported to FDA as a well-controlled study in support of a new indication for use, nor intended to be used to support any other significant change in the labeling for the drug.
- (2) The investigation is not intended to support a significant change in the advertising for a prescription drug product.
- (3) The investigation does not involve a change in route of administration, dosage level, or patient population, or other factor that significantly increases the risks (or decreases the acceptability of risks) associated with use of the drug product.
- (4) The investigation is conducted in compliance with the requirements for institutional review (21 CFR 56) and informed consent (21 CFR 50).
- (5) The investigation is conducted in compliance with the requirements of 21 CFR 312.7, i.e., the drug may not be represented as safe or effective, nor may it be commercially distributed, for the purposes for which it is under investigation.

4.3 Drug storage/ handling and administration:

Cilostazol and placebos will be provided by the Fairview IDS pharmacy and preloaded into the 1 month pill box and given or shipped to the patient after consent is obtained.

The pill box has 31 removable medication vials for each day of the month to simplify the administration schedule and increase adherence. The study always starts at the first day of a month.

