4.4 Biosafety: N/A

4.5 Stem Cells: N/A

4.6 Fetal Tissue: N/A

## 5.0 Procedures Involved

5.1 Study Design: prospective single blind placebo controlled n=1 study with 2 cross-overs

5.2 Study Procedures:

- NTproBNP on cilostazol and on placebo (see flow diagram) day 5 to 7 (5mL's) and day 25 to 28 (5 mL's) at any Fairview Lab site.
- Kansas City Heart Failure Questionnaire (KCCQ-12) will be administered by PI phone call day 7, 14, 21 and 28
- Baseline patient characteristics collected from Fairview EPIC

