## **11.0 Local Recruitment Methods**

*11.1* Recruitment Process: Potential patients determined to be possible candidates will be approached in the clinic and/or Hospital. The environment will be conducive to discussion as the patient will be seen privately in a clinic exam room, or in a private exam room. Distractions are kept to a minimum. The visit will occur in a relaxed and open atmosphere conducive for private conversation.

Subjects will be given time to think over whether or not they want to participate in the study. Subjects are free to discuss their options with their primary care or physician and their family members before making their decision.

*11.2* Identification of Potential Participants: Potential subjects will be recruited based on information contained in private/protected records (medical records, student records). This also includes subjects who will be recruited from the PI or Co-I's patient population. The PI and Co-Investigators have legitimate access to records per their employment with UMP heart and Fairview hospitals/clinics. Research staff checks for opt-outs and does not review records if the patient has opted out.

Research team members have legitimate access to records by virtue of their employment. Study team members, such as coordinators, are allocated this authority per the Delegation of Authority log. Please note, all involved research staff member have undergone required PHI and Human Subjects training for the

UMN, MHEALTH and Fairview in order to safely, correctly and legitimately access medical records.

Initial contact with potential participants would be made by the treating cardiology providers followed by PI or Co-investigators. A physician or care provider in the cardiology clinic or on the cardiology service will briefly tell the patient about the study and ask if they would like to discuss it further with a member of the research staff (one of the investigators or coordinators). If the patient agrees, a member of the study staff will meet with the patient and discuss the study in more detail.

Potential subjects will come from the UMP Cardiology Clinic/Cardiology Inpatient/Outpatient service where the cardiology provider practice, PI and Co-Investigators clinically manage these patients.

Private/protected records will include MEDICAL records. Research staff will ensure the patient has not opted out of research on the Consent for Treatment and Registration form.

*11.3* Recruitment Materials: N/A

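### Inpatients may be enrolled and started on the next first of the month with no stability requirement, so any recovery from the admission would fall wholly into the NTproBNP contrast (KCCQ much less)

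*Combined protocol and SAP*

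**What the plan says.** **Where patients come from.** Section 8.0 (Screening) states: "Individuals will be screened or assessed for eligibility during a hospital admission at the UMN Medical Center or in the UMP cardiology outpatient clinics". Section 11.1 agrees: "Potential patients determined to be possible candidates will be approached in the clinic and/or Hospital". Step 1 of the study flow in section 4.1 mentions clinic patients only.

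**When they start.** Section 4.3: "The study always starts at the first day of a month". Nothing links day 1 to discharge. The study flow runs from consent to drug distribution to start. It describes no run-in and no KCCQ or NTproBNP measurement before treatment.

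**What the criteria require.** The one hospitalization item in section 8.0 is a way to qualify, "HFpEF >50% hospitalization in the last 3 years", with no minimum time since the admission. Pulmonary edema or loop diuretic use also qualifies. No exclusion concerns recent discharge or a recent diuretic change, and the NYHA 3 and 4 exclusion is tied to an LVEF below 50%. The nearest entry in section 9.1 excludes an "Individual or group that is approached for participation in research during a stressful situation such as emergency room setting, childbirth (labor), etc". That protects against coercion and says nothing about clinical stability.

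**What is measured.** Under section 5.2, KCCQ-12 is taken on days 7, 14, 21 and 28. NTproBNP is drawn on "day 5 to 7 (5mL's) and day 25 to 28 (5 mL's) at any Fairview Lab site", once on each treatment. Section 2.2 expects that cilostazol "lowers NTproBNP by about 25% to suggest a clinical benefit".

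**Order and analysis.** Section 4.1 gives one order: cilostazol, placebo, cilostazol, placebo. Section 15.3 models a binary start order. No randomization of order is described, and neither the paired tests nor the mixed model has a week or period term.

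**The concern.** A design in which patients are their own controls assumes that, apart from treatment, the condition stays level for the whole month. A patient discharged on the 29th and dosed on the 1st satisfies every written rule. The first blood draw would then come about a week after discharge and the second about three weeks later. If NTproBNP is falling because the patient is recovering, that fall is counted as a treatment difference. It hides a benefit when cilostazol comes first and imitates one when placebo comes first.

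The individual results are at stake as well as the group mean. Section 7.1 tells each participant whether they benefited and, on request, involves the treating provider in a discussion of prescribing. Balancing the order across patients does not correct a single patient's contrast.

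**Working it through.** **The plan's own figure.** Section 15.2 gives KCCQ 71 with SD 19 and a 25% relative difference, so the target is 0.25 × 71 = 17.75 points. With two-sided alpha 0.05 (assumed; not stated) and 80% power, 2 × (1.960 + 0.842)² × 19² / 17.75² = 17.99, which rounds up to 18. The stated 18 reproduces, by a parallel-group formula. The sample size is not in dispute here; 17.75 is used only as a yardstick.

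**Assumed inputs (not in the documents).** Share of patients still recovering, p = 0.25 to 0.50. Fall in NTproBNP between the two draws from recovery alone, f = 0.10 to 0.30. KCCQ gain from week 1 to week 4 in an affected patient, 3 to 15 points.

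**NTproBNP, mean effect.** With weekly periods, the draws fall in week 1 and week 4, which are on different treatments under either alternating order. The mean log drift is d = p × ln(1 − f). If the true cilostazol/placebo ratio is R, the observed ratio is R × exp(−d) with cilostazol first and R × exp(d) with placebo first. With cilostazol first:

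| p | f | exp(−d) | Observed ratio if R = 0.75 | Apparent reduction | Apparent change if R = 1 |
|---|---|---|---|---|---|
| 0.25 | 0.10 | 1.027 | 0.770 | 23.0% | +2.7% |
| 0.50 | 0.20 | 1.118 | 0.839 | 16.1% | +11.8% |
| 0.50 | 0.30 | 1.195 | 0.896 | 10.4% | +19.5% |

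With placebo first, the first and last rows turn a true 0.75 into 0.731 and 0.627, and no effect into 0.974 and 0.837.

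**NTproBNP, one affected patient.** With cilostazol first, a 25% recovery fall exactly offsets a 25% drug effect: 0.75 / 0.75 = 1.00. With placebo first and no drug effect, the same fall gives 0.75, which is the effect the protocol expects.

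**NTproBNP, added spread under balanced order.** Without a period term, an affected patient contributes +|ln(1 − f)| or −|ln(1 − f)| depending on sequence, and the others contribute 0. The mean is zero and the SD is |ln(1 − f)| × √p. For f = 0.30, |ln 0.7| = 0.357, which gives 0.178 at p = 0.25 and 0.252 at p = 0.50. A period term would reduce this to 0.357 × √(p(1 − p)) = 0.154 to 0.178, but the plan has none. The random effect for sequence does not do this job, because it shifts all of a patient's values equally.

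**KCCQ.** With a steady gain of b points per week, the four weeks carry 0, b, 2b and 3b. In the cilostazol-first order the cilostazol mean is (0 + 2b)/2 = b and the placebo mean is (b + 3b)/2 = 2b, so the contrast is biased by −b. A gain of 3 to 15 points over the three steps gives b = 1 to 5 points per affected patient (1.1 to 5.7 if recovery is front-loaded). If half the sample is affected, the mean bias is 0.5 to 2.5 points. The sign reverses with placebo first.

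**The case against.** The strongest reply is that the drift is inferred. The documents do not give the inpatient share, the time from discharge to day 1, or the size of any recovery. Section 8.0 speaks of a hospital admission, not a heart failure admission, and the study flow refers to clinic patients, so the affected share may be small. Stable patients on loop diuretics, or with an admission up to three years back, also meet the qualifying items, and some patients will wait most of a month before starting. All of this stands. It limits the size of the problem, but nothing in the plan requires recovery before day 1.

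A reader might infer that KCCQ is distorted as badly as NTproBNP. The schedule does not support that. Four alternating weekly scores cancel most of a steady drift, and the questionnaire is the primary outcome in section 1.2.

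A reader might also infer a systematic bias against cilostazol. That needs a single or unbalanced order. Section 4.1 describes one order, while section 15.3 implies two. If order is balanced, the mean bias cancels and the cost is extra variance. If the SD of the paired log ratio were 0.4 to 0.6 (assumed), adding 0.18 in quadrature would raise it by about 4% to 10%, and adding 0.25 by about 8% to 18%. So the missing randomization and period term share the blame with the entry rule. Repairing them would still leave the individual results exposed.

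**Conclusion.** The point holds as a conditional weakness, mainly for NTproBNP. The text establishes that inpatients may be enrolled, that the calendar alone sets the start, that no stability criterion, run-in or baseline measurement is described, and that a single week-1 to week-4 pair has nothing to cancel a drift. The text does not establish that recovery will occur in these patients, or how much.

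Under the assumed ranges, the expected 25% reduction would be seen as about 23% to 10% if everyone starts on cilostazol, and the null as a 3% to 20% increase. Under balanced order, the cost is an added SD of about 0.18 to 0.25 log units for a 30% fall, in a study planned on 18 completers. For KCCQ, the residual of 1 to 5 points per affected patient is small against 17.75. This does not invalidate the primary comparison, but it is worth correcting because the correction is cheap.

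**What to change.** Add to section 8.0 a stability requirement before day 1: no recent heart failure admission and no recent loop diuretic change. The investigators should set and state the interval, since the documents give no basis for a particular length. Patients found in hospital may still be consented there; their pill box would start on the first of a later month that meets the rule.

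Heart failure admissions and diuretic changes on days 1 to 28 may be recorded and described. They should not be used to exclude patients from a repeat analysis, because treatment may influence them and the sample is small. Recording them would be a new data item, since section 5.2 takes only baseline characteristics from EPIC.

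The entry rule costs a protocol wording change, a delayed start for patients found in hospital, and the loss of a few of them. Recruitment of stable outpatients should hardly be affected.

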## **10.0 Local Number of Participants**

*10.1* Local Number of Participants to be Consented: 25

## **11.0 Local Recruitment Methods**

*11.1* Recruitment Process: Potential patients determined to be possible candidates will be approached in the clinic and/or Hospital. The environment will be conducive to discussion as the patient will be seen privately in a clinic exam room, or in a private exam room. Distractions are kept to a minimum. The visit will occur in a relaxed and open atmosphere conducive for private conversation.

Subjects will be given time to think over whether or not they want to participate in the study. Subjects are free to discuss their options with their primary care or physician and their family members before making their decision.

*11.2* Identification of Potential Participants: Potential subjects will be recruited based on information contained in private/protected records (medical records, student records). This also includes subjects who will be recruited from the PI or Co-I's patient population. The PI and Co-Investigators have legitimate access to records per their employment with UMP heart and Fairview hospitals/clinics. Research staff checks for opt-outs and does not review records if the patient has opted out.

Research team members have legitimate access to records by virtue of their employment. Study team members, such as coordinators, are allocated this authority per the Delegation of Authority log. Please note, all involved research staff member have undergone required PHI and Human Subjects training for the

UMN, MHEALTH and Fairview in order to safely, correctly and legitimately access medical records.

Initial contact with potential participants would be made by the treating cardiology providers followed by PI or Co-investigators. A physician or care provider in the cardiology clinic or on the cardiology service will briefly tell the patient about the study and ask if they would like to discuss it further with a member of the research staff (one of the investigators or coordinators). If the patient agrees, a member of the study staff will meet with the patient and discuss the study in more detail.

Potential subjects will come from the UMP Cardiology Clinic/Cardiology Inpatient/Outpatient service where the cardiology provider practice, PI and Co-Investigators clinically manage these patients.

Private/protected records will include MEDICAL records. Research staff will ensure the patient has not opted out of research on the Consent for Treatment and Registration form.

*11.3* Recruitment Materials: N/A

*11.4* Payment: N/A

